Improving Holding Function of the Hemiplegic Hand with Chemodenervation

NCT02459951

Date: 4-29-2016

Improving Holding Function of the Hemiplegic Hand with Chemodenervation

Specific Aims

Inserting and holding an object in the hand is what we mean by 'hand as a holder' function. After a stroke, the hand typically lacks voluntary finger extension that opens the hand. Simultaneously, the hand is also subjected to involuntary contraction of finger flexor muscles that close the hand, resulting in clenched fist and thumb-in-palm deformities. Despite these typical hemiplegic configurations, persons with stroke may be able to insert an object into the hand by wiggling and pushing it into the hemiplegic hand with their uninvolved hand, though struggle is often present and failure is frequent. A main goal of this project is to demonstrate that 'hand as a holder' function can be improved by blocking overactive muscles with medication. The main measure of hand function improvement will be 'transit time' i.e. the time it takes for the uninvolved hand to insert an object into the hemiplegic clenched fist and hold it independently.

This pilot study of 9 patients aims to demonstrate reliability and validity of a digital video method that will be used to measure 'transit time'. It also aims to establish initial statistical support for improved object transit time into the hemiplegic clenched fist after Botox A injections. [Botox A, injected directly into offending muscles, is a neuromuscular blocking agent that was approved by the FDA in 2010 to treat spasticity, a form of involuntary muscle contraction, in finger and wrist flexor muscles of persons sustaining a hemiplegic stroke.]

Experimental Design

Study hypothesis: Given hemiplegic patients, of stroke etiology, with a neurally driven clenched fist, who may also have a thumb-in-palm and/or a flexed wrist and who have severely impaired voluntary finger and thumb extension, we hypothesize that 'hand as a holder' function will improve after chemodenervation of relevant finger, thumb and wrist muscles selected by clinical examination.

The study objective is a pilot demonstration of the clinical hunch that objects will be inserted for holding by the hemiplegic hand more quickly and easily after chemodenervation, and, in some cases, insertion of larger diameter objects will be achieved as well.

Inclusion Criteria

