The log-transformed Transit Times were analyzed using a linear mixed effects (LME) model with the fixed effects of cylinder diameter (0.5, 1, 1.5, 2, 2.5 inches), evaluation session (Pre 1, Pre 2 and Post Treatment) and their interaction. The random effects of subject and evaluation session were included to allow for correlation among repeated measures for the same participant. Though two statistical models were considered, the model reported here included Pre2 and Post-treatment Transit Times as repeated measures of response variable, and Pre1 Transit Times as a covariate in the model, using the average of the three cylinder insertion trials for each cylinder diameter and evaluation session. The residuals of the LME model were evaluated for consistency with the assumption of the normal distribution.

The data included 69 (17%) of trials with missing transit times meaning that a subject was not able to do the insertion. A linear mixed effects methodology is appropriate for modeling data with missing observations if the ‘misses’ (i.e. participant was unable to insert a cylinder into the affected hand within 30 seconds) are ignorable or missing at random. For non-ignorable ‘misses’, it is required to specify the response mechanism (a probability model for missing indicator or non-response). A repeated measures logistic regression model was used to model the missing data indicator and investigate whether the ‘misses’ depended on cylinder diameter, evaluation session or Transit Times observed at the first baseline session (Pre1).

The data analysis was performed in SAS (SAS Institute Inc., Cary, NC, USA) and R (R Core Team (2016). R: A language and environment for statistical computing. R Foundation for Statistical Computing, Vienna, Austria. URL <http://www.R-project.org/>.)

Protocol 2: The counts of successful holds (i.e. participants had to hold a given cylinder independently with the affected hand for 5 seconds) in 3 trials for each cylinder diameter were modeled using a repeated measures negative binomial model with the 3 trials as an exposure.

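### The primary Post/Pre2 transit-time ratio is conditional on successful insertion: time-limit misses are not missing at random, and the miss model described cannot repair that

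*Combined protocol and SAP*

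**What the plan says.** Statistical Methods, Protocol 1, analyses log transit times with a linear mixed model. For the responses, "the model reported here included Pre2 and Post-treatment Transit Times as repeated measures of response variable", with Pre1 times as a covariate, "using the average of the three cylinder insertion trials for each cylinder diameter and evaluation session". The Post/Pre2 geometric ratio is the primary outcome.

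On missing times the same section reports: "The data included 69 (17%) of trials with missing transit times meaning that a subject was not able to do the insertion". It makes the mixed model conditional on the misses being harmless ("participant was unable to insert a cylinder into the affected hand within 30 seconds) are ignorable or missing at random"). For misses that are not, "it is required to specify the response mechanism (a probability model for missing indicator or non-response". It then describes one check: "A repeated measures logistic regression model was used to model the missing data indicator and investigate whether the" misses depended on diameter, session or the Pre1 time.

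Failures are expected by design. Specific Aims says of unaided insertion, "though struggle is often present and failure is frequent". Experimental Design expects that after treatment, "in some cases, insertion of larger diameter objects will be achieved as well". Project Design sets a 30-second trial and ends the transit time at release into an independent hold, which must last 5 seconds. Protocol 2 models the number of successful holds out of three trials as a separate, secondary outcome.

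**The concern.** The analysed variable is a time, so a trial without one contributes nothing to the mixed model. If the trial has no time because the participant was still working at the limit, the unobserved value is known to be long. That is right-censoring. Treating such a trial as simply missing discards the information that it was slow, and whether it is missing depends on the very value that is not seen. The condition that the plan sets for its own model then fails for those trials.

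The logistic model does not close this gap. It can show that misses relate to diameter, session or Pre1 time. It cannot show that, given those, they are unrelated to the unobserved time. Nor is it joined to the transit-time model, so it corrects nothing in the ratio.

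At stake is the main estimate of a pilot meant to give initial statistical support. If treatment turns slow failures into slow successes, those slow times enter the Post average while their Pre2 counterparts are absent.

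**Working it through.** **1. The plan's own figure.** Project Design gives 9 participants, 3 sessions and 15 trials per session: 9 × 3 × 15 = 405, and 69/405 = 17.04%, which matches the stated 17%. The total of 405 is derived, not stated. Denominators from 395 to 418 would round to 17%, and 405 is the only full-design total among those tried (8 participants: 360, 19.2%; 10 participants: 450, 15.3%).

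**2. The share that bears on the ratio.** The responses are Pre2 and Post only: 9 × 2 × 15 = 270 trials. The 69 misses are not split by session. All could lie in Pre1 (135 trials), so the share in these 270 runs from 0% to 69/270 = 25.6%.

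**3. Closed-form illustration.** Assume log-normal times, every miss a time above 30 s, and log SD σ. With miss share p in a session, put a = z(1 − p) and λ = φ(a)/(1 − p). The session mean of log time is log 30 − σa, and the mean among successes is lower by σλ. Hence
- true log ratio = −σ(a_Post − a_Pre2)
- log ratio from successes = true log ratio − σ(λ_Post − λ_Pre2)

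Take σ = 0.8 and an assumed split of 29/28/12 (Pre1/Pre2/Post), which sums to 69:
- Pre2: p = 28/135 = 0.207, a = 0.815, λ = 0.361
- Post: p = 12/135 = 0.089, a = 1.348, λ = 0.177
- true: −0.8 × (1.348 − 0.815) = −0.426, ratio 0.653
- from successes: −0.426 + 0.8 × (0.361 − 0.177) = −0.278, ratio 0.757

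Other assumed splits at σ = 0.8:

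| Misses Pre1/Pre2/Post | True ratio | Ratio from successes |
|---|---|---|
| 23/23/23 | 1.000 | 1.000 |
| 26/26/17 | 0.801 | 0.869 |
| 20/20/29 | 1.226 | 1.131 |

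For σ of 0.5, 0.8 and 1.1 and the unequal splits tried, 61% to 69% of the true log ratio is retained.

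**4. The plan's model, simulated.** A mixed model can recover part of the loss from the other trials of the same participant, so step 3 may overstate the bias. Simulated trials used these assumptions, none of which the documents supply:
- log-SDs for subject, session within subject, subject by diameter, and trial of 0.6/0.2/0.2/0.5, 0.7/0.2/0.3/0.6 (middle set) and 0.9/0.3/0.3/0.8
- 0.25 log units per diameter step, overall misses set at 17%, every miss a time-limit miss
- cell means taken over successful trials, and rows without a Pre1 value dropped

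| True ratio, same at all diameters | Mixed-model estimate |
|---|---|
| 1.0 | about 1.0 |
| 0.70 | about 0.76 to 0.78 |
| 0.50 | about 0.58 to 0.61 |

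One set of middle-set runs gave 0.77 and 0.58 for true 0.70 and 0.50. The bias is ln(0.77/0.70) = 0.095 and ln(0.58/0.50) = 0.148 log units, against a run-to-run SD of 0.10 to 0.12. The retained share of the log ratio is 0.261/0.357 = 73% and 0.545/0.693 = 79%.

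**5. An uneven effect.** With the middle set and no effect in the hardest half of the subject-by-diameter cells, a true mean ratio of 0.70 gives 0.70 and 0.57 gives 0.56. The attenuation is gone. These runs were repeated and agreed.

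**6. What counts as a miss.** Protocol 1 defines a miss by insertion within 30 s. Project Design ties the end of a transit time to an independent 5-second hold. The documents do not say whether an inserted but dropped cylinder is among the 69, whether the 30 s run from first contact, or whether they include the hold.

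**The case against.** The plan does not ignore the problem. It names the condition, says what is needed if it fails, and models the miss indicator. It says that two models were considered and describes one, so the text does not prove that no alternative was run; it shows only that none is described. Failures have their own outcome in Protocol 2, and a time outcome paired with a success outcome is a recognised two-part design. The study is a small, exploratory pilot. In the even-effect illustration the bias is conservative, and with no effect the estimate stays near 1.0. The absence of logistic results from a methods text is a reporting matter.

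Most of that stands, and it limits the point. It does not remove it. The successful-holds outcome cannot show how far the time ratio depends on the excluded trials, and a check on observed predictors cannot establish the condition.

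A reader might infer three stronger things that the documents do not support:
- **That all 69 misses are censored times.** Some may be cylinders that could not enter the fist at all, which have no finite time to censor. Experimental Design expects some larger cylinders to become insertable only after treatment.
- **That the ratio is known to understate the effect.** Misses are not given by session, diameter or reason, and step 5 shows that the attenuation can disappear.
- **That 17% of the trials behind the ratio are missing.** The 17% includes Pre1.

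The obvious remedy also has a weakness. Censoring trials in which insertion was impossible can create an apparent speed-up, and excluding them conditions on success again.

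**Conclusion.** The point holds in limited form. The primary ratio is conditional on successful insertion. The plan's condition for the mixed model fails for every miss that is a time-limit failure, and the logistic model can neither establish nor repair it. The actual size and direction of any bias cannot be determined from the documents.

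With an even effect, log-normal times, the assumed variances and time-limit misses only, the estimate is pulled toward 1 by roughly one run-to-run SD at a true ratio of 0.70, and by somewhat more at 0.50. With no effect, bias is negligible in the same setting. The matter should be fixed, because the label and table are cheap and the estimate is the one this pilot exists to provide. Confidence is medium, since every size quoted rests on assumed variances and an assumed mix of misses.

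**What to change.** 1. Label the primary ratio 'given successful insertion' and interpret it jointly with the successful-holds outcome.
2. Tabulate misses by session, diameter and, where the video allows, reason: time limit reached, could not be entered, not held for 5 seconds. Reconcile the definitions of a miss in Project Design and Protocol 1.
3. Keep the mixed model as primary. Add a post hoc sensitivity analysis: a trial-level mixed model of log transit time, with time-limit misses right-censored at the time elapsed from first contact to the end of the trial. Do not set failed holds to 30 s. Fit the same trial-level model with misses simply dropped, so that the contrast reflects the missing-data handling and not the change of model. Report cells that could not be entered under the success outcome, and show the ratio with them censored and with them excluded. State that the first can overstate speed-up and that the second is itself conditional on success.
4. Report the range of these results, not a single corrected ratio.

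The cost is a wording change, classification of 69 trials from recordings (assuming they were kept) and re-analysis of existing data. The sensitivity analysis is post hoc, depends on log-normality in the tail, and may be hard to fit with 9 participants. If it does not fit, items 1 and 2 still stand.

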9 participants with spastic hemiparesis greater than 12 month's duration will be studied using a repeated measures design. Two baseline sessions separated by at least 3 days will be conducted along with one post Botox treatment session, approximately 3 to 5 weeks later. [The peak response of Botox for spasticity has been reported as 4 weeks (1). Our clinical experience also confirms that four weeks is a reasonable time to expect a treatment effect. However, practical considerations such as participant schedules and transportation encourage us to target 4 weeks 7 days.] Each participant will use their uninvolved hand to insert cylinders with 5 graduated diameters into the receiving hemiplegic hand. The same scripted instructions will be used for all participants, including visual demonstration of cylinder insertion through the web space entrance of the hand. Cylinder diameters will range between 0.5 and 2.5 inches and will be approximately similar in weight and height. Each session will consist of 15 trials (5 cylinder diameter sizes times 3 insertions for each diameter → 15 trials, the order of diameter size being randomized). A 30 second trial duration will be allotted. Three synchronized Sony AS100VR recording cameras will provide side, front and top views, strategically placed to observe the "onset" time i.e. time of

initial object contact with the hemiplegic hand and the “offset” time i.e. the time the uninvolved hand lets go of the cylinder and the hemiplegic hand holds the cylinder independently. [The hemiplegic hand must visibly be holding the object independently for 5 seconds without being dropped or otherwise supported by contact with other parts of the body or the environment.] Using Final Cut Pro video software, playback of the synchronous views of the three cameras will be used by two independent coders to measure onset and offset times in order to calculate object transit time. Given that all insertions will be video recorded, it may be useful for coders to score qualitative aspects of performance when a participant doesn't meet the 5-sec criterion of unsupported grasp. In addition, we are unaware of another measure of holding function that could be administered to test convergent validity, emphasizing one aspect of the novelty of this project's work.

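### The reported transit-time model and the check on misses both use Pre1 transit time, which does not exist where every Pre1 trial was missed, and no rule for that case is given

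*Combined protocol and SAP*

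**What the plan says.** The design (Project Design) is: "9 participants with spastic hemiparesis greater than 12 month's duration will be studied using a repeated measures design". Each person attends twice before injection (Pre1 and Pre2) and once after it (Post). "Each session will consist of 15 trials (5 cylinder diameter sizes times 3 insertions for each diameter", and "A 30 second trial duration will be allotted".

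Under Statistical Methods, Protocol 1:

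- A failed insertion is recorded as a missing transit time: "The data included 69 (17%) of trials with missing transit times meaning that a subject was not able to do the insertion".
- The section opens with a mixed model in which session has three levels (Pre1, Pre2, Post). It then says two models were considered. The one reported has Pre2 and Post as responses and "Pre1 Transit Times as a covariate in the model". It works on the three-trial average for each diameter and session.
- The mixed model is said to suit data with missing observations if the misses are ignorable or missing at random.
- One check is described: a repeated measures logistic model asking whether misses "depended on cylinder diameter, evaluation session or Transit Times observed at the first baseline session (Pre1".

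The primary outcome is the geometric ratio of transit time from Pre2 and Post. Protocol 2 counts successful holds out of three trials at all three sessions, as a secondary outcome. No rule is given for a missing Pre1 value.

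**The concern.** The missing-at-random argument for a mixed model concerns missing responses. It does not cover a missing covariate: a row with no Pre1 value is left out unless the analyst does something about it. A cell (one participant at one diameter) with three Pre1 misses therefore takes its Pre2 and Post rows out of the reported model, even where both were observed. It also leaves any logistic fit that includes Pre1 time.

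These cells are not a random subset. They are the combinations the participant could not do at first baseline, so they are where later misses are most likely. They are also where a new ability would show. The study objective (Experimental Design) includes the hope that "in some cases, insertion of larger diameter objects will be achieved as well". A diameter failed at Pre1 and achieved at Post cannot enter the primary ratio from the reported model.

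**Working it through.** **1. The plan's own figure.** 9 participants × 3 sessions × 15 trials = 405 trials. 69/405 = 17.04%, which agrees with the stated 17%.

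**2. Units at risk.** 9 participants × 5 diameters = 45 cells per session, so the reported model has at most 45 × 2 = 90 Pre2 and Post responses. Each cell without a Pre1 time costs up to 2 of the 90.

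**3. Bounds without a model.** If *k* of the 69 misses fell at Pre1 and available trials are averaged, at most *k*/3 cells, rounded down, have no Pre1 time.

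| Misses at Pre1 | Most cells with no Pre1 time |
|---|---|
| 0 | 0 |
| 23 (one third) | 7 of 45 (7/45 = 16%) |
| 34 (about half) | 11 of 45 |
| 69 (all) | 23 of 45 |

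The minimum can be 0 even with 23 Pre1 misses, since at two per cell they fit into 12 cells. If instead an average needs all three trials, 23 Pre1 misses remove between 8 (23/3, rounded up) and 23 cells. The documents do not say which averaging rule applied. If available trials were averaged, a cell with one or two Pre1 misses stays in, with a mean over its successes only.

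**4. Likely size, by simulation.** The documents give no SDs, so these are assumptions. Log time = mean + person effect + diameter slope + log(0.70) at Post + trial error. A trial is a miss if its time exceeds 30 s, and the mean is tuned to about 17% misses overall. The between-person SD is of the order of 0.4 to 0.8 and the trial SD 0.4 to 0.7, on the log scale.

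| Quantity | Range |
|---|---|
| Cells with no Pre1 time | about 2 to 5 of 45 |
| Share of Pre2 misses in those cells | 13% to 48% |
| Share of Post misses in those cells | 15% to 63% |
| Those cells with at least one Post success | 57% to 89% |

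The low end arises when trial noise is large relative to differences between people. A separate simulation added a person-by-diameter effect and used true ratios of 0.5 to 0.8. It gave about 4 to 6 cells. Between 49% and 63% of Pre2 misses stayed visible to a model that includes Pre1 time, so 37% to 51% did not.

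**5. Does moving Pre1 to the response side correct the estimate?** With a true ratio of 0.70, the covariate model gave 0.74 to 0.78. The three-session model gave 0.74 to 0.79, with a sampling SD about 3% smaller. With no true effect, both models gave 1.00. So the move recovers observed data and a little precision. The shift towards 1 comes from misses at Pre2 and Post, which stay missing in either model.

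**6. Does dropping the cells hide dependence in the miss model?** In an example under similar assumptions, restricting to the retained cells changed the session coefficient from -0.80 to -0.94. The diameter coefficient went from 1.37 to 1.16, a fall of 0.21/1.37 = 15%. Across settings the Pre1 coefficient stayed large, at 2.0 to 3.6 per log unit. Strong dependence would still be seen.

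**The case against.** The strongest reply is that deletion is inferred. The plan does not say how a missing Pre1 value was treated, nor whether the logistic predictor is a cell-level or a participant-level time. The wording of the check allows the three predictors to be tested separately, and fits on diameter or session alone would keep every trial. This stands, so the point is limited to fits that include Pre1 time, run by default.

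Three stronger readings are tempting, and the documents do not support them:

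- *That the check is biased towards showing little dependence.* Step 6 does not show this. Nor could the check settle ignorability in either direction: misses that depend on diameter, session or observed Pre1 time are compatible with missing at random given those variables. The plan says only that dependence was investigated. It reports no result and does not conclude that the misses are ignorable.
- *That new successes are lost to the study.* Protocol 2 counts them by diameter at every session. They are absent only from the primary ratio.
- *That using Pre1 as a response level repairs the estimate.* Step 5 shows it does not.

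It is also fair to say that the problem is tied to censoring at 30 s. If every session were a censored response, or misses were scored at 30 s, no cell would lack a usable Pre1 value. That is why the two remedies belong together.

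**Conclusion.** The gap is real. Both models use a quantity that is undefined in cells wholly missed at Pre1, the plan gives no rule for them, and its missing-at-random argument does not reach a missing covariate. Run by default, fits with Pre1 time lose a small number of cells that carry a disproportionate share of later misses.

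The actual count is unknown. Arithmetic allows 0 to 23 of 45 cells if available trials are averaged; the assumed SDs suggest the ranges in step 4. No false-positive risk was found. The shift towards no effect seen in simulation cannot be attributed to the missing covariate, because it persists when Pre1 becomes a response.

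A reader might infer that the primary result is invalid. The documents do not support that: the loss is unquantified, the secondary analysis keeps these successes, and the study is a 9-person exploratory pilot. This should be fixed, but it is not a condition for using the results.

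**What to change.** 1. **Miss model.** Replace Pre1 transit time with the number of Pre1 successes out of 3 for that diameter (0 to 3), which is defined whether or not any Pre1 insertion succeeded. Fit it to all Pre2 and Post trials. Leave out Pre1 trials, where the predictor would determine the outcome. Describe the result as showing what misses depend on, not as proof that they are ignorable.
2. **Transit-time model.** Report the three-session model, with Pre1 as a level of session, so that no observed Pre2 or Post value is lost through a missing Pre1. Pair it with an analysis that treats each miss as right-censored at 30 s, since the first step alone leaves the bias from Pre2 and Post misses in place.
3. **Reporting.** Tabulate the 69 misses by session and diameter. State the averaging rule and how a missing Pre1 value was handled. Give the number of cells, and of misses, that the reported models dropped.

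The cost is re-running models on existing data, with no new measurements. The sponsor should expect that misses may prove to depend strongly on baseline ability.

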The predictors of expected number of successful holds included the cylinder diameter and evaluation session (Pre-1 baseline session, Pre-2 baseline session, and Post-treatment). The interaction between cylinder diameter and evaluation session was also considered, but was not a significant predictor of mean successful holds. The model allowed for correlation among counts for multiple cylinder diameters and evaluation sessions for the same participant using an exchangeable correlation structure. Correlation among counts was estimated using the GEE approach (as implemented in SAS PROC GENMOD, SAS Institute Inc., Cary, NC, USA).

Primary Outcome Measure(s):

1. Geometric Ratios of Log-transformed Transit Time [Time Frame: transit times were measured at Pre-injection session 2 and Post-injection session]

Secondary Outcome Measure(s):

2. Incidence Rate of Successful Holds [Time Frame: evaluation sessions Pre1, Pre2, and Post]

3. Incidence Ratio of Successful Holds [Time Frame: evaluation sessions pre1, pre2, and post]

4. Modified Ashworth Scores (MAS) for injected muscles [Time Frame: evaluation sessions Pre1, Pre2, and Post]; [MAS are obtained to verify that a biological effect of neurotoxin is, indeed, present] .

Subject Recruitment Plan: The MCAL treats over 400 patients a year and clenched fist problems occur in 20%. We anticipate no difficulty in obtaining 9 participants for this pilot study.

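### The secondary hold-count GEE rests on 9 participants with no small-sample correction described, and on one reading its interaction test could not have rejected

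*Combined protocol and SAP*

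**What the plan says.** The Data Analysis Plan (Statistical Methods, Protocol 2) models the number of successful holds out of three, per diameter and session, with a "repeated measures negative binomial model with the 3 trials as an exposure". Predictors are diameter and session. Counts from the same participant share an exchangeable correlation, and "Correlation among counts was estimated using the GEE approach (as implemented in SAS PROC GENMOD". On the interaction it reports: "The interaction between cylinder diameter and evaluation session was also considered, but was not a significant predictor of mean successful holds".

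The number of clusters is small: "This pilot study of 9 patients aims to demonstrate reliability and validity". On sessions, Project Design says "Two baseline sessions separated by at least 3 days will be conducted along with one post Botox treatment session"; on trials within a session, "5 cylinder diameter sizes times 3 insertions for each diameter".

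The incidence rate and incidence ratio of holds are both listed as secondary outcomes, over Pre1, Pre2 and Post. For this model the text does not give the standard error type, the test (score or Wald), the reference distribution, the alpha, the diameter coding or any small-sample correction.

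**The concern.** GEE inference with sandwich standard errors relies on a large number of independent clusters. Nine is few, however many counts each contributes. Two consequences matter.

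- **Session ratios.** If normal-reference inference was used, p-values and intervals for the incidence ratio of holds may not have their stated error rates, and a borderline secondary result could be misread.
- **Interaction.** The main-effects model gives one session ratio for all cylinder sizes. Yet the study objective itself anticipates that some participants will manage wider objects after treatment, so an effect that varies with diameter is a question the trial raises. If the interaction test had no means of rejecting, its non-significance cannot support the single ratio.

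**Working it through.** **Number of clusters.** Planned trials: 9 participants × 3 sessions × 15 trials = 405. Protocol 1 says "The data included 69 (17%) of trials with missing transit times", and 69/405 = 17.0%, which reproduces the stated figure. Eight participants would give 69/360 = 19.2% and ten 69/450 = 15.3%, so 9 fits. Each participant supplies 5 × 3 = 15 hold counts.

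**Degrees of freedom.** Session has 2 df. With five diameter categories the interaction has 4 × 2 = 8 df; with linear diameter it has 1 × 2 = 2 df.

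**Bound on the score test.** Let v_i be participant i's contribution to the interaction score, and let V stack the nine rows. The generalised score statistic is T = (Σv_i)′(Σv_i v_i′)⁻¹(Σv_i) = 1′V(V′V)⁻¹V′1. This is the squared length of a projection of a vector of nine ones, so T ≤ 9. No assumption about hold rates enters.

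| Diameter coding | df | 5% critical value | Smallest possible p at T = 9 |
|---|---|---|---|
| Five categories | 8 | 15.51 | 0.342 |
| Linear | 2 | 5.99 | 0.011 |

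The 8-df score test needs at least 16 participants before it can reach 5%. The 2-df test can reject but is conservative (simulated size 1.1–2.4%).

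**8-df robust Wald test.** This is no substitute. By normal theory, Hotelling's statistic with 9 units and 8 dimensions is (8 × 8/1)·F(8,1) = 64·F(8,1), and the uncorrected sandwich multiplies it by 9/8. Size is P(64·F(8,1) > 15.51 × 8/9) = 93.7%. Two sets of simulations gave about 81–95%.

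**Session ratios: normal-theory benchmark.** For a within-participant contrast with an uncorrected sandwich standard error and z, size is P(|t₈| > 1.96 × √(8/9)) = P(|t₈| > 1.848) = 10.2%.

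**Session ratios: simulation.** The documents give no hold rates or variances, so these are assumed. The main set used 9 participants × 15 binomial(3) counts; mean hold rate 83%, 70% or 50%; logit-normal participant SD 1.0 or 1.5; participant-by-session SD 0, 0.5 or 1.0; a linear diameter effect of 0.4 logit per step; and no session effect. The fit was a log-link exchangeable GEE with Poisson working variance (negative binomial at zero dispersion): 18 scenarios × 4,000 datasets. Two further sets used similar assumptions.

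| Nominal 5% test | False rejection |
|---|---|
| Post vs Pre2, sandwich, z | 7.1–9.6% (main set); 8.1–9.0% and about 6–12% (further sets) |
| Post vs Pre2, sandwich, t(8) | 3.1–5.4% (main set); 4–5.5% (one further set) |
| Post vs Pre2, model-based, z | about 0–17%, by session-to-session variance and hold rate |
| Overall session, sandwich, χ²(2) | 11.4–15.1% |
| Overall session, sandwich, F(2,8) | 4.5–7.7% |

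**Cost of t(8).** 2.306/1.960 = 1.177, so intervals are 17.7% wider; a statistic of 1.96 moves from p = 0.050 to p = 0.086.

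**The case against.** The strongest reply is that everything depends on unstated choices. Protocol 2 does not say that sandwich standard errors, a normal reference, a score test or categorical diameter were used. It names no Post versus Pre2 contrast for holds; only the primary transit-time measure is tied to those two sessions. It also does not say that non-significance was the sole reason for the main-effects model. The study is an exploratory pilot and holds are secondary.

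Most of this stands, and it limits the claim. A reader might infer that the reported hold result does reject too often, or that the interaction test was bound to fail. The documents support neither as fact. With model-based standard errors the error can go either way: in one set of six scenarios false rejection was 0–4% in five and 16% in the sixth. With linear diameter the interaction test could have rejected. The 8-df Wald fault, over-rejection, is not what happened, since the reported result was non-significant.

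What survives is that neither common standard error with a normal reference is dependable at 9 participants, while the sandwich with t(8) stayed near 5% in the scenarios tried. The score bound is algebra and does not depend on the assumed rates.

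**Conclusion.** The point holds as a cheap improvement to a secondary analysis.

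- **Session ratios.** Under assumed hold rates, sandwich standard errors with z give about 6–12% false rejection against a nominal 5%. Model-based standard errors give about 0–17%. The direction of any error in the actual analysis is unknown.
- **Interaction.** Only if a generalised score test with five diameter categories was used is p ≥ 0.342 guaranteed; the non-significance is then no evidence for a common ratio. If diameter was linear, the result carries some information, though non-significance still does not establish a common ratio.

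An alpha of 0.05, two-sided, is assumed throughout. Nothing here shows that the reported hold findings are wrong.

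**What to change.** 1. State the standard error type, test, reference distribution and diameter coding for the hold model.
2. Use the sandwich standard error with a t(8) reference for the session incidence ratios, and F(2,8) for the overall session test.
3. Do not rest the single ratio on non-significance of the interaction. Report diameter-specific hold rates and ratios descriptively.
4. If an interaction test is wanted, use a 1-df linear-diameter-by-session (Post versus Pre2) term on the model's log scale, with sandwich standard error and t(8). Its size was not simulated here and should be checked before use.

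A tempting shortcut for step 4 is each participant's slope over diameter of the raw Post minus Pre2 count. It should not be used. It tests additivity, whereas an incidence ratio is multiplicative: if hold rates fall with diameter, a true common ratio still makes the count differences slope. In three simulated scenarios with a steep fall in hold rate and a true common ratio, it rejected 16%, 41% and 73% of the time.

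**Cost.** A few lines of code on existing data. Intervals widen by about 18%. For an assumed Post effect of +1 logit, nominal power is 12–17 points lower with t(8) than with z, part of which is only the inflated error rate of z. F(2,8) may stay slightly liberal (up to 7.7%). A 1-df term sees only a linear trend over diameter, so its non-significance would not prove a common ratio either.
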